**Table 11.4-1 Criteria for Potentially Clinically Significant Electrocardiograms**

Parameter	Unit	Higher Limit
QRS interval	msec	QRS $\geq 115$ msec (2-5 (inclusive) years)
PR interval	msec	PR $> 225$ msec (2-5 (inclusive) years)
QTc(F)	msec	$>480$

QTc(F) = QT Corrected by Fridericia's formula

## 11.5 POTENTIAL HY'S LAW

*Potential* Hy's Law criteria within a 24-hour window is defined by a post baseline elevation of ALT or AST  $\geq 3$  x ULN, along with TBL  $\geq 2$  x ULN and a non-elevated ALP  $< 2$  x ULN, all based on blood draws collected within a 24-hour period.

Participants who meet the potential Hy's Law criteria from the first dose of study drug to within 30 days after the last dose of study intervention will be summarized. Supportive tabular displays will also be provided.

**12.0            HEALTH OUTCOMES ANALYSES**

Not applicable.

**13.0            INTERIM ANALYSIS**

There is no planned interim analysis of efficacy in this study.

**13.1            DATA SAFETY MONITORING BOARD**

An independent DSMB will review unblinded interim safety data at defined intervals throughout the study. After at least 6 participants in Cohorts 1 to 3 complete at least 2 weeks of double-blind study intervention, the independent DSMB will review unblinded interim safety data. Based on this review, the DSMB will recommend whether the subsequent planned dose level should be tested. Further details of the DSMB (composition, policy, and procedures) are specified in a separate DSMB Charter.

**14.0 DETERMINATION OF SAMPLE SIZE**

Up to 30 participants, 2 to 5 years of age, will be sequentially enrolled into LIN-MD-67; 8 participants each into Cohorts 1 to 3 will be randomly assigned with 3:1 allocation ratio either to linaclotide dose or matching placebo and 6 additional participants in the final cohort will be randomly assigned with 5:1 allocation ratio either to linaclotide dose or matching placebo. Participants will be randomly assigned to receive linaclotide or matching placebo as described in Section 4.0.

Sample size in this study is not driven by any statistical consideration. Instead, this study is designed to enroll sufficient pediatric participants to observe the clinical response trends and monitor safety.

**15.0 STATISTICAL SOFTWARE**

Statistical analyses will be performed using version 9.3 (or newer) of SAS on a Linux operating system.

## **16.0 DATA HANDLING CONVENTIONS**

### **16.1 VISIT TIME WINDOWS FOR SAFETY ANALYSES**

Table 16.1–1 presents the visits assigned for safety analyses and the corresponding range of study intervention days (window) during which an actual visit may occur.

**Table 16.1–1 Visit Time Windows**

Derived Visit	Scheduled Visit Daya	Window
Baseline	Day 1	Days ≤ 1
Week 2 Visit	Day 15	Days [2, 21]
Week 4 Visit	Day 29	Days [Day 22, max (last dose day+1, Visit 5 date)]
Postintervention Visit	Day 36	Days ≥ max (last dose day+1, Visit 5 date)+1
End of Double-Blind Intervention Period b	Final or Termination Visit during the double-blind Intervention Period	

a Relative to the date of the first dose of double-blind study intervention. Day 1 = the date of the first dose of double-blind study intervention. There is no Day 0 or Week 0.

b Presented in analysis tables for safety parameters, including but not limited to electrocardiograms, clinical laboratory values, and vital signs.

If the assessment date (if the assessment date is unavailable, use visit date instead) is on or after the date of the first dose of study intervention, the study day is calculated by assessment date – date of the first dose of study intervention + 1. If the assessment date is before the date of the first dose of study intervention, the study day is calculated by assessment date – date of the first dose of study intervention. Therefore, a negative day indicates a day before the start of the study intervention.

If a participant has 2 or more visits within the same window, the last visit with a non-missing value will be used for analysis.

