- The participant must complete at least 4 weeks (28 days) of study intervention before returning for Visit 5 (Week 4). The last dose of study intervention will be administered at the study site at the Visit 5 (Week 4) visit on Day 29 (+2) at approximately the same time as on other days of study intervention administration. Caregivers will be instructed when the participants should fast to ensure they have fasted for at least 2 hours before receiving their last dose of study intervention (Section 10.8.3)
- All randomized participants who prematurely discontinue from the study, regardless of cause, are required to be seen for the assessments completed at EOT (Visit 5, Week 4), except for PK sample collection.
- The parent/guardian/legally authorized representative must provide written informed consent before the participant's enrollment in the study. If a parent or legal guardian is also the participant's caregiver, he or she will be asked to sign a combined parent and caregiver written informed consent. Caregivers other than parent or legal guardian must provide written informed consent.
- Prior to dosing, the investigator or appropriate site staff member will assess if Rome IV criteria for Child FC was met and record the outcome in the eCRF. Eligibility for the study is not based on this assessment.
- Participants in Cohorts 1-3 will be randomized on Study Day 1 (Visit 3) at a 1:3 ratio to either a predose or postdose PK sample respectively. The 6 additional participants in the final cohort will be randomized at a 1:2 ratio to either a pre-dose or post-dose PK sample, respectively (Section 8.5.1).
- Physical examinations will be performed by medically qualified site personnel at Screening (Visit 1) and Week 4 (Visit 5) and may be repeated at the investigator's discretion. If fecal impaction (as defined in footnote h below) is documented during an optional repeat physical examination, the study physician must be notified.

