### 11.3 VITAL SIGNS

Descriptive statistics for vital signs (ie, temperature, body weight, respiratory rate, supine pulse rate, supine systolic and diastolic blood pressure) and changes from baseline values at each assessment time point will be presented by study intervention group within the corresponding cohort.

Vital sign values will be considered PCS if they meet both the observed-value criteria and the change-from-baseline criteria listed in [Table 11.3–1](#). The number and percentage of participants with PCS postbaseline values will be tabulated by study intervention group within the corresponding cohort for the double-blind Intervention Period and Postintervention Period separately. The percentages will be calculated relative to the number of participants with available non-PCS baseline values and at least 1 postbaseline assessment in the specific period. The numerator will be the total number of participants with available non-PCS baseline values and at least 1 PCS postbaseline value during the specific period for the corresponding cohort. A supportive tabular display of participants with PCS postbaseline values will be provided, including the PID number, baseline and all postbaseline (including non-PCS) values.

In addition, a tabular display showing all AEs that occurred in participants who had PCS postbaseline vital sign values will be provided.

If any cohort has a similar linaclotide dose with another cohort, the above discussed vital signs summaries will also be provided combining participants from the similar dose cohorts. Summaries will also be provided for participants from all cohorts in the placebo group.

Table 11.3-1 Criteria for Potentially Clinically Significant Vital Signs

Parameter	Flag	Criteria a	
		Observed Value	Change From Baseline
Systolic Blood Pressure, mmHg - Postural Vital Signs (Supine and Standing)		Decrease in systolic blood pressure of 20 mmHg or more from supine to standing [*Change from supine SBP <= -20]	Decrease in systolic blood pressure from supine to standing at observed time point is at least 10 mmHg greater than the decrease in systolic blood pressure from supine to standing at baseline [Postbaseline change from supine SBP – baseline change from supine SBP <= -10]

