**Table 16.2–1 Analysis Time Windows for Efficacy Analysis - Daily Questions**

Period	Analysis Week	Beginsa	Endsa
Preintervention (Baseline b )	Week -2	Day -14	Day -8
	Week -1	Day -7	Day 1, time of randomization
Intervention	Week 1	Day 1, time after randomization	Day 7
	Week 2	Day 8	Day 14
	Week 3	Day 15	Day 21

Period	Analysis Week	Begins a	Ends a
	Week 4	Day 22	Day of last dose
Postintervention	Post-treatment	Day of last dose + 1	Day of end of study visit

Note: On randomization day, any eDiary assessment prior to randomization time will be part of the Preintervention Period and any eDiary assessment after randomization time will be part of double-blind study intervention period.

a Relative to the date of randomization; Day 1 = the day of randomization.

b Baseline values for efficacy parameters will be derived from the daily eDiaries and eCRF data collected in the Preintervention Period, specifically the period of time from 14 days before randomization up to the time of randomization.

For the Intervention Period, daily diary day is calculated as (diary date - date of randomization + 1). For the Preintervention Period, daily diary day is calculated as (diary date - date of randomization). However, the day of randomization is study Day 1 regardless. Caregivers will complete the diary entries once per day for daily diary.

If a participant withdraws during the Intervention Period, the participant's Intervention Period for daily diary responses shall end at the day of the last dose. The impacted Intervention Period week shall be shortened to the end of the withdrawn participant's Intervention Period and all subsequent Intervention Period weeks will be missing for that participant.

**Table 16.2-2** below presents the weekly periods assigned for the efficacy analysis of the weekly diary data related to global severity of symptoms and global change in symptoms.

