**16.4 REPEATED OR UNSCHEDULED ASSESSMENTS OF SAFETY PARAMETERS**

If a participant has repeated assessments before the start of the first study intervention, the results from the final non-missing assessment made prior to the start of the study intervention will be used as baseline as appropriate unless specified. If end-of-study assessments are repeated or if unscheduled visits occur, the last non-missing postbaseline assessment will be used as the end-of-study assessment for generating summary statistics. However, all postbaseline assessments will be used for PCS value determinations, and all assessments will be presented in the data listings.

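### The Week 2 safety window is not cut at end of treatment, so for very early discontinuers it overlaps Postintervention and an off-drug value can become the Week 2 result

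*SAP*

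**What the plan says.** SAP Table 16.1-1 assigns safety assessments to derived visits by study day:

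- Week 2 is Days 2 to 21, with no reference to when treatment ended.
- Week 4 is "Days [Day 22, max (last dose day+1, Visit 5 date" (closing brackets left off here), so it stops at end of treatment.
- Postintervention is "Days ≥ max (last dose day+1, Visit 5 date)+1".
- A further row, End of Double-Blind Intervention Period, takes the final or termination visit in that period and has no day limits.

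The rule under the table is "If a participant has 2 or more visits within the same window, the last visit with a non-missing value will be used for analysis".

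Visit 5 can come early. Protocol 1.3 states: "All randomized participants who prematurely discontinue from the study, regardless of cause, are required to be seen for the assessments completed at EOT". Visit 6 is scheduled 7 days (+2) after the Week 4/EOT visit.

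Three other places in the SAP bear on the point:

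- Section 16.2 says that, on withdrawal, "the participant's Intervention Period for daily diary responses shall end at the day of the last dose". That covers diary data only.
- Section 16.4 says that, with repeated or unscheduled visits, "the last non-missing postbaseline assessment will be used as the end-of-study assessment for generating summary statistics". It also uses all postbaseline assessments for PCS determinations and shows all of them in listings.
- Section 11.3 tabulates vital-sign PCS values "for the double-blind Intervention Period and Postintervention Period separately", but does not say where one period ends and the other begins.

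**The concern.** Week 4 and Postintervention share a boundary that moves with each child's end of treatment. Week 2 does not use it. A child who stops early and is seen again by Day 21 therefore has an assessment that satisfies both the Week 2 and the Postintervention rows. No sentence says which row wins or limits Week 2 to on-treatment assessments. Under the tie rule, the later, off-drug assessment is then the one summarised at Week 2, and the value taken nearer the last dose drops out of that summary.

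At stake is whether the Week 2 by-visit safety summaries describe children on treatment. Repeat testing makes this more than a matter of chance. Protocol 8.2.4 has clinically significant laboratory values repeated until they return to normal or baseline, or stop being clinically significant, so taking the last value in the window tends to favour a recovered one. Two programmers could also assign the same visit differently and both claim to follow the SAP.

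**Working it through.** There is no sample size, power or alpha figure to reproduce. The check applies the windows as written.

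**Inputs.** L = day of last dose; V5 = study day of Visit 5; d = day of a later assessment (SAP Table 16.1-1). Visit 6 = V5 + 7 to V5 + 9 (Protocol 1.3). Cohorts 1-3 have 8 children at 3:1, that is 6 linaclotide and 2 placebo (SAP 4.0).

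**Cut-off.** Let E = max(L + 1, V5), or L + 1 if Visit 5 is not held. Then Week 2 is 2 ≤ d ≤ 21, Week 4 is 22 ≤ d ≤ E, and Postintervention is d ≥ E + 1.

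**Completers.** Visit 4 on Day 15 is in Week 2 only. Visit 5 on Days 29-31 is in Week 4 only. Visit 6 on Days 36-40 is in Postintervention only. The table works as intended for them.

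**When windows overlap.** Week 4 and Postintervention cannot overlap, since one ends at E and the other starts at E + 1. Week 2 and Postintervention overlap when E + 1 ≤ d ≤ 21. This requires E ≤ 20, so L ≤ 19 and V5 ≤ 20 (or no Visit 5), with a further assessment by Day 21.

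**Through a scheduled Visit 6.** V5 + gap ≤ 21 gives:

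- gap 7: V5 ≤ Day 14
- gap 8: V5 ≤ Day 13
- gap 9: V5 ≤ Day 12

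**Examples.**

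- L = 6, V5 = 8, Visit 6 = 15. E = max(7, 8) = 8, so Postintervention starts on Day 9. Day 15 is in both windows and, being last, replaces Day 8 as the Week 2 value. It is 15 − 6 = 9 days after the last dose.
- L = 13, V5 = 15, Visit 6 = 22. Day 22 is past Day 21, so it is in Postintervention only and there is no conflict.

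**Enumeration.** Over L = 1-31, V5 from L to Day 44, and d = 1-59, Week 2 with Postintervention was the only overlap found (1,520 combinations), and no day fell in no window. With Week 2 ended at min(21, E), there were 0 overlaps and 0 gaps on the same grid. Visit 5 itself never overlaps, because Postintervention starts after it.

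**Weight of one child.** If all children in the arm have a Week 2 value, swapping one child's value for another that differs by D moves the arm mean by D/6 (linaclotide) or D/2 (placebo) in Cohorts 1-3. The documents give no basis for choosing D.

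**The case against.** The other side has four good arguments.

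**The safety signal is not lost.** A reader might infer that an abnormal value near the last dose is overwritten throughout the safety results. It is not. Under SAP 16.4 all postbaseline assessments count for PCS determinations and appear in listings. The End of Double-Blind Intervention Period row, on its natural reading, still reports the EOT value. This stands, and limits the clear effect to the by-visit descriptive summaries. A reader might also expect the Week 2 mean of the postural pulse change to be distorted. SAP 11.3 plans by-visit statistics for supine pulse and blood pressure, temperature, respiratory rate and weight. Protocol 9.4.2.3 adds standing values, but neither document plans a by-visit mean of the supine-to-standing change.

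**Double counting in the PCS tables is not shown.** A reader might infer that one off-drug value is counted in both the Intervention and the Postintervention vital-sign PCS tables. That would follow only if the visit windows define the periods, which the SAP does not say. What remains is an undefined boundary.

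**The route is narrow.** The protocol requires discontinuers to have the EOT assessments but does not clearly require them to attend Visit 6. Visit 6 schedules vital signs but no laboratory tests or ECG, so those are affected only by repeat or unscheduled tests. Cases may also be rare. The protocol's account of its two earlier pediatric studies reports 2 discontinuations for diarrhea among 214 linaclotide-treated children. At that rate, at most 6 + 6 + 6 + 5 = 23 linaclotide children here would give 23 × 2/214 ≈ 0.2. That rate comes from older children, covers only one reason for stopping and is not confined to early stops, so it is a rough guide. It still supports expecting few cases.

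**Another reading is open.** A programmer could assign such visits to Postintervention alone, since that row starts where treatment or Visit 5 ends. That is sensible, but the SAP does not say it, and the tie rule applied literally to the Week 2 row gives the other answer.

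**Conclusion.** The windows are wrong as written, but the scope is small and the point is minor. Table 16.1-1 places some off-drug assessments in both Week 2 and Postintervention, and the last-visit rule read literally makes the off-drug value the Week 2 result. This concerns only children with last dose by Day 19, Visit 5 by Day 20 or not held, and another assessment by Day 21.

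The effect falls on by-visit descriptive summaries, mainly of supine vital signs, temperature, respiratory rate and weight. The documents do not support a claim that PCS findings are lost or that PCS values are in fact counted twice. No dropout rate is given, so the number of children cannot be estimated from the plan. The case for acting rests on arm size: in Cohorts 1-3 one child is 1/6 of a linaclotide arm or 1/2 of a placebo arm.

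The conclusion assumes that discontinuers are seen again by Day 21, either at Visit 6 or for an unscheduled or repeat assessment.

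**What to change.** In SAP Table 16.1-1, change the Week 2 window to Days [2, min(21, max(last dose day+1, Visit 5 date))]. Add a sentence that assessments after max(last dose day+1, Visit 5 date) belong only to Postintervention, and state that the same cut-off separates the two periods in the vital-sign PCS tables of Section 11.3. Say also that the cut-off is last dose day+1 when Visit 5 is not held.

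This applies the SAP's own Week 4 boundary to Week 2 and leaves completers' assignments unchanged. An EOT visit held off drug by Day 21 would still sit in Week 2, which the existing Visit 5 term in the cut-off appears to intend. The cost is one edited table row and a short note, with no change to data collection or study conduct.

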## **16.2 VISIT TIME WINDOWS FOR EFFICACY ANALYSES**

Table 16.2–1 below presents the analysis weeks assigned for the efficacy analysis of the participant daily diary data related to BM symptom characteristics. These analysis weeks will be used in the calculations for all week-based endpoints (eg, SBM weekly frequency rate, stool consistency weekly scores, etc.).

**Table 16.2–1 Analysis Time Windows for Efficacy Analysis - Daily Questions**

Period	Analysis Week	Beginsa	Endsa
Preintervention (Baseline b )	Week -2	Day -14	Day -8
	Week -1	Day -7	Day 1, time of randomization
Intervention	Week 1	Day 1, time after randomization	Day 7
	Week 2	Day 8	Day 14
	Week 3	Day 15	Day 21

Period	Analysis Week	Begins a	Ends a
	Week 4	Day 22	Day of last dose
Postintervention	Post-treatment	Day of last dose + 1	Day of end of study visit

Note: On randomization day, any eDiary assessment prior to randomization time will be part of the Preintervention Period and any eDiary assessment after randomization time will be part of double-blind study intervention period.

a Relative to the date of randomization; Day 1 = the day of randomization.

b Baseline values for efficacy parameters will be derived from the daily eDiaries and eCRF data collected in the Preintervention Period, specifically the period of time from 14 days before randomization up to the time of randomization.

For the Intervention Period, daily diary day is calculated as (diary date - date of randomization + 1). For the Preintervention Period, daily diary day is calculated as (diary date - date of randomization). However, the day of randomization is study Day 1 regardless. Caregivers will complete the diary entries once per day for daily diary.

If a participant withdraws during the Intervention Period, the participant's Intervention Period for daily diary responses shall end at the day of the last dose. The impacted Intervention Period week shall be shortened to the end of the withdrawn participant's Intervention Period and all subsequent Intervention Period weeks will be missing for that participant.

**Table 16.2-2** below presents the weekly periods assigned for the efficacy analysis of the weekly diary data related to global severity of symptoms and global change in symptoms.

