**Table 4-1**      **Schedule of Evaluations: Study LIN-MD-67**

Schedule of Evaluations LIN-MD-67						
Study Periods (Duration)	Screening (14-28 Days)	Preintervention (14-21 Days)	Study Intervention (29 Days)			Postintervention (7 Days)
	Screening a	Preintervention	Randomization b	Week 2	Week 4/EOT c,d	1 Week Postintervention Visit End of Study
Study Visit	1	2	3	4	5	6
Study Day			1	15 ( $\pm$ 2)	29 (+ 2)	Week 4/EOT + 7 (+2)
Parent/LAR/Caregiver Consent e	X					
Inclusion and Exclusion Criteria	X	X	X			
Modified Rome III Assessment	X				X	
Assess Rome IV status f			X			
IWRS	X	X	X		X	
PK Random Assignment in IWRS g				X		
Medical History	X					
Lifestyle Modification Information Given to Caregiver	X					
Physical Examination h	X				X	
Fecal Impaction Assessment i	X	X j	X j			
Height	X					
Vital Signs, Postural Vital Signs k	X	X	X	X	X	X
ECG	X				X	
Clinical Laboratory Tests l	X				X	
PK Sample g					X m	
AE Evaluation	X	X	X	X	X	X
Prior and Concomitant Medications	X	X	X	X	X	X
Dispense Rescue Medication n		X	X	X	X	
eDiary and Instructions Given to Caregiver o		X				
eDiary Eligibility Report p			X			
eDiary Compliance o			X	X	X	X
Study intervention administered in the clinic			X b		X c	
Study intervention dispensed			X			

Schedule of Evaluations LIN-MD-67						
Study Periods (Duration)	Screening (14-28 Days)	Preintervention (14-21 Days)	Study Intervention (29 Days)			Postintervention (7 Days)
	Screening a	Preintervention	Randomization b	Week 2	Week 4/EOT c,d	1 Week Postintervention Visit End of Study
Study Visit	1	2	3	4	5	6
Study Day			1	15 ( $\pm$ 2)	29 (+ 2)	Week 4/EOT + 7 (+2)
IP and Rescue Medication Compliance and Accountability				X	X	X e

- a During the Screening Period, caregivers will receive information regarding lifestyle modifications. There should be at least a 2-week interval between discussing the lifestyle modifications during the Screening Period and the participant's entry into the Preintervention Period.

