**6.3 MODIFIED INTENT-TO-TREAT POPULATION**

The Modified Intent-to-Treat (mITT) Population will consist of all Randomized Population who receive at least 1 dose of double-blind study intervention and who had at least 1 postbaseline entry on bowel movement (BM) characteristic assessments that determine occurrences of spontaneous bowel movements (SBMs) (ie, BM frequency and rescue medication use). Participants will be summarized according to the randomized study intervention for all efficacy analyses.

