## **10.0            EFFICACY ANALYSES**

The efficacy analyses will be based on the mITT Population.

Baseline values for efficacy endpoints related to daily eDiary responses will be derived from the eDiary in the Preintervention Period, specifically the time period from 14 days before randomization up to the time of randomization.

A SBM is a BM that occurs in the absence of laxative, suppository, or enema use on the calendar day of the BM or the calendar day before the BM. Caregiver-observed SBMs are defined as SBMs reported in the eDiary for which the caregiver identified being with the child for.

Baseline SBM weekly rates, stool consistency for caregiver-observed SBMs, and straining for caregiver-observed SBMs will be derived as discussed in Section 16.3 from 14 days prior to randomization and up to the time of randomization. A participant's baseline stool consistency and straining reported for caregiver-observed SBMs cannot be assessed if the participant does not have at least 1 caregiver-observed SBM during the Preintervention Period. For participants with no caregiver-observed SBMs reported in the eDiary during a study period, the consistency and straining assessments reported by caregiver will be considered missing for that study period in the analyses. Participants with missing baseline consistency and straining reported by the caregiver will be excluded from the respective consistency and straining change from baseline analyses.

Baseline value for the global severity in symptoms will be based on the last non-missing assessment on or before the date of first dose of study intervention.

An observed-cases approach to missing postbaseline data will be applied. Efficacy analyses will be performed via descriptive summary statistics in terms of mean, median, SD, standard error of mean, minimum, and maximum. No statistical testing will be performed to compare linaclotide dose with placebo. No multiplicity adjustment will be applied in this dose-ranging study.

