### **10.1        KEY EFFICACY ENDPOINTS**

There are 4 key efficacy endpoints in this study.

- Change from Baseline in 4-Week Overall SBM Frequency Rate (SBMs/week) During the Study Intervention Period of Each Cohort**

The SBM rate per week during the Study Intervention Period will be derived based on the total number of SBMs reported by a caregiver as being directly observed by the caregiver during this period in the eDiary, as discussed in Section 16.3.4.

Descriptive statistics (mean, median, SD, standard error of mean, minimum, and maximum) will be provided by study intervention group for each cohort as main analysis approach. The sensitivity descriptive statistics will also be provided by first imputing the postbaseline missing daily data during Study Intervention Period with the worst response for caregiver-observed SBM (i.e. assuming 'Yes' response for missing rescue medication use).

Descriptive summary statistics similar to main analysis approach will be provided for change from baseline in 4-week overall SBM frequency rate including the SBMs not directly observed by the caregiver.

- **Change from Baseline in 4-Week Stool Consistency Reported by the Caregiver During the Study Intervention Period of Each Cohort**

Stool consistency for caregiver-observed SBMs will be derived as discussed in Section 16.3.5. Descriptive statistics (mean, median, SD, standard error of mean, minimum, and maximum) will be provided by study intervention group for each cohort.

- **Change from Baseline in 4-Week Straining Reported by the Caregiver During Study Intervention Period for Each Cohort**

Straining for caregiver-observed SBMs will be derived as discussed in Section 16.3.6. The summary statistics for this key efficacy endpoint will be provided by study intervention group in the similar way as discussed for change from baseline in 4-week stool consistency reported by the caregiver during Study Intervention Period for each cohort.

- **Proportion of Days With Fecal Incontinence During Study Intervention Period (For Participants Who Have Acquired Toileting Skills During Daytime and Nighttime or Acquired Toileting Skills During Daytime Only) Within Each Cohort**

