#### *Stool Frequency Rates*

The components for calculating a participant's stool frequency rates (SBM weekly rates) for a given period are as follows:

- The number of BMs that occurred during that specific period
- The number of those BMs that were SBMs
- The number of days during that specific period:
- Randomization day will be considered as a half day for the double-blind Intervention Period and Preintervention Period.

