#### *Duration of an Analysis Week*

With respect to a participant's scheduled analysis weeks, the term duration is used. In regard to the duration of a week, it is expected that 1 or more of a participant's "weeks" may not be exactly 7 days in duration (eg, a participant may withdraw or discontinue early from the trial or may have missing diary day). Deviations from the 7 days norm are structural in nature; and, as such, the calculations of the weekly rates of SBMs will incorporate the actual days contributed within the time period (week or specific phase).

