### ***Weekly Stool Frequency Rate Calculations***

The weekly frequency rate for SBMs will be based on the total number of SBMs reported by a caregiver as being directly observed by the caregiver based on the diary entries during that time period, adjusting for differences in the length of the time period. Weekly stool frequency rates for each specific period will be calculated as follows:

$$\text{Weekly Frequency Rate (Specific Period)} = \frac{\text{Total number of SBMs reported by a caregiver as being directly observed during the specific time period}}{\text{Number of days during the specific analysis period}} \times 7$$

The weekly frequency rate for SBMs will also be derived based on the total number of SBMs occurring based on the diary entries during that time period (including SBMs not directly observed by the caregiver), adjusting for differences in the length of the time period.

Weekly Frequency Rate (Specific Period) including SBMs not directly observed by caregiver =

$$\frac{\text{Total number of events (SBMs) during the specific period}}{\text{Number of days during the specific period}} \times 7$$

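### Does a child who stops in the first days distort the 4-week SBM mean in a way the plan leaves open?

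*SAP*

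**What the plan says.** The SBM endpoint is built from five rules in the SAP.

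- **Rate (16.3.4).** "The weekly frequency rate for SBMs will be based on the total number of SBMs reported by a caregiver as being directly observed". That count is divided by days and multiplied by 7.
- **Days (16.3.4).** "Randomization day will be considered as a half day for the double-blind Intervention Period and Preintervention Period", and the "calculations of the weekly rates of SBMs will incorporate the actual days contributed within the time period".
- **Withdrawal (16.2, text under Table 16.2–1).** The child's "Intervention Period for daily diary responses shall end at the day of the last dose". The table assigns the days after last dose to the Postintervention window. The same paragraph says the child's later Intervention Period weeks are missing.
- **Population (6.3).** A child needs one dose and must be one "who had at least 1 postbaseline entry on bowel movement (BM) characteristic assessments". No minimum number of diary days is set.
- **Missing data (10.0, 10.1, 16.3.1, 16.3.2).** "An observed-cases approach to missing postbaseline data will be applied". Missed diaries are not imputed unless the SAP says so. A missing rescue-medication answer in an incomplete diary counts as no use. The sensitivity analysis works by "first imputing the postbaseline missing daily data during Study Intervention Period with the worst response for caregiver-observed SBM", and a parenthesis in the same sentence explains this as taking a missing rescue-medication answer to be Yes.

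**The concern.** The endpoint is called a 4-week rate, yet a child treated for three days enters the mean with the same weight as a completer. That child's rate rests on 2.5 days instead of 28.5. In an arm of five or six, one such child could carry the mean and its standard error, and dose response is a stated objective read only from these descriptive statistics.

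The one planned missing-data sensitivity analysis refers to the Study Intervention Period without saying, in SAP 10.1, where that period ends for a withdrawn child. The schedule in SAP Table 4-1 heads the period as 29 days, while the diary windows end it at last dose. If the two readings gave different tables, the choice could be made after unblinding. On the shorter reading, no planned summary would cover the days after stopping.

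**Working it through.** **1. Arm sizes (SAP 14.0).** 3 × 8 + 6 = 30, as stated. Linaclotide: 8 × 3/4 = 6 in each of Cohorts 1 to 3 and 6 × 5/6 = 5 in the final cohort, so 3 × 6 + 5 = 23. Placebo: 2 + 2 + 2 + 1 = 7.

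**2. Weight of one SBM.** Days = last-dose day − 0.5; one SBM is worth 7 / days.

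| Last dose | Days | One SBM, per week |
|---|---|---|
| Day 1 | 0.5 | 14.0 |
| Day 3 | 2.5 | 2.8 |
| Day 7 | 6.5 | 1.08 |
| Day 15 | 14.5 | 0.48 |
| Day 29 | 28.5 | 0.25 |

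The leverage is real, but it belongs to the first days and has largely gone by Day 15.

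**3. Effect on the mean.** The documents give no SD or expected rate, so these inputs are assumptions: six children, baseline 1.5 SBMs/week, the other five averaging +1.5 (sum 7.5).

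- Day 3 stop, two SBMs: 2 / 2.5 × 7 = 5.6; change +4.1; mean (7.5 + 4.1) / 6 = 1.93.
- Day 3 stop, six SBMs: 16.8; change +15.3; mean (7.5 + 15.3) / 6 = 3.80. If the five completers are spread from +0.5 to +2.5 in steps of 0.5, the SE is 2.32 but the median is only 1.75.
- Day 1 stop, one SBM: 14; change +12.5; mean 3.33.
- Day 1 stop, no SBM: change −1.5; mean 1.00.

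For a less selected picture, assume Poisson counts at a true 3/week. The 5th to 95th percentile shift that one child causes in a six-child mean is −0.50 to +0.90 for a Day 3 stop and −0.50 to +0.58 for a Day 7 stop. A completer already causes −0.21 to +0.24. Where the final cohort shares a dose with an earlier one, SAP 10.1 also pools them. With 6 + 5 = 11 children the Day 3 range narrows to −0.27 to +0.49. Shifts occur in both directions.

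**4. The two readings of the sensitivity analysis.** For the Day 3 child with two SBMs:

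- Period ends at last dose: the rate stays 5.6 and the arm mean 1.93.
- Period runs to Day 29, later days scored as no SBM: 2 / 28.5 × 7 = 0.49; change −1.01; mean (7.5 − 1.01) / 6 = 1.08.

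The readings differ, so the question is which one the text supports.

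**5. What the text supports.**

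- Table 16.2–1 is the SAP's window definition for daily diary data. The sensitivity analysis imputes daily data, so this table governs it, and it closes the period at last dose. The 29 days in Table 4-1 are a heading in a visit schedule.
- The parenthesis in SAP 10.1 names the response being imputed: rescue medication taken. That reverses the default in 16.3.2, so the analysis tests that default. Assumed rescue use removes spontaneous status from a recorded bowel movement. A day with no diary has no recorded movement to reclassify.
- The longer reading therefore needs a step the SAP does not state: adding 29 − 3 = 26 uncontributed days to the denominator. That runs against the actual-days rule in 16.3.4 and the bar on imputing missed diaries in 16.3.1.

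**6. How often.** Protocol 2.2.2 reports 214 children treated with linaclotide (116 + 16 + 74 + 8 = 214) and two discontinuations for diarrhea. 2 / 214 × 23 = 0.21 expected over all four weeks. Both were aged 12 to 17; the younger groups had no discontinuation for an adverse event.

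**The case for a change.** The strongest counter-argument rests on the withdrawal paragraph itself. After closing the period, it calls the child's later Intervention Period weeks missing, and missing data are what SAP 10.1 says it imputes. A programmer could follow that to the longer reading, and 1.93 against 1.08 is not trivial in a six-child arm. This leaves a slight ambiguity. But the sentence follows the one that ends the period, and its natural purpose is the weekly summaries, where a Day 3 stopper simply has no value for Weeks 2 to 4.

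A second argument is that 0.2 understates early stops. It counts only diarrhea discontinuations, comes from older children, and Protocol 4.2 acknowledges the lack of data in this age group. Protocol 7.1.1 also requires discontinuation for related serious events. Withdrawn children are not replaced, and placebo groups of two or one per cohort are more exposed than the linaclotide arms. All of that is fair, and the true rate is unknown. It does not show a bias, and all seven placebo children are also summarized together.

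A third is that no planned summary estimates a full four weeks including time off drug. On the last-dose reading that is true. It asks for a different estimand, which nothing in the documents requires. Filling the later days with the baseline rate would put an assumption in place of any real diary entries after last dose and pull every early stopper toward no change. Statisticians would disagree about whether that is better.

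**Conclusion.** The concern does not hold. The arithmetic is sound, but it describes a known property of a rule the SAP states openly: observed cases, actual days, period ending at last dose. The means of 3.80 and 3.33 need extreme patterns, such as six observed SBMs in 2.5 days from a child with a baseline of 1.5 per week. The assumed Poisson range for a Day 3 stop is −0.50 to +0.90 in a six-child arm, with no directional bias shown.

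No decision rule or error rate depends on this mean. SAP 10.0 rules out testing, SAP 14.0 gives no statistical basis for the sample size, and SAP 13.1 ties progression to DSMB review of safety data. SAP 7.0 and 10.1 already provide the median, minimum, maximum, cumulative distribution plots, weekly summaries, same-dose pooling and a listing of discontinuations, so such a child would be visible.

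The scope of the sensitivity analysis follows from reading SAP 10.1 with 16.2 and 16.3. What is left is at most an absent cross-reference. The illustrated sizes rest on assumed baseline rates, assumed changes and a Poisson count; the conclusion rests on the text of the plan.
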